Health condition(s) or problem(s) studied	Dysphonia (arising from muscle tension dysphonia, presbylaryngis and vocal fold palsy)
Study Type i.e. Cohort etc	Feasibility study
Target sample size	30 (10 of each condition)
STUDY TIMELINES	
Study Duration/length	18 Months
Expected Start Date	January 2020
End of Study definition and anticipated date	When 30 participants have been recruited and have taken part, or 18 months have elapsed, whichever comes first.
Key Study milestones	Securing of funding, JRO submission, first patient recruitment, study close.
FUNDING & Other	
Funding	[name], Clinical Research Specialist, CHEM Smith's Medical , [name]
Other support	N/A
STORAGE of SAMPLES (if applicable)	
Data collected / Storage	N/A
KEY STUDY CONTACTS	Full contact details including phone, email and fax numbers
Chief Investigator	[name] [contact] Tel/[contact]

KEY ROLES AND RESPONSIBILITIES

SPONSOR: The sponsor is responsible for ensuring before a study begins that arrangements are in place for the research team to access resources and support to deliver the research as proposed and allocate responsibilities for the management, monitoring and reporting of the research. The Sponsor also has to be satisfied there is agreement on appropriate arrangements to record, report and review significant developments as the research proceeds, and approve any modifications to the design.

FUNDER: The funder is the entity that will provide the funds (financial support) for the conduction of the study. Funders are expected to provide assistance to any enquiry, audit or investigation related to the funded work.

PRINCIPLE INVESTIGATOR (PI): The person who takes overall responsibility for the design, conduct and reporting of a study, ensuring that the study is conducted as per the approved study protocol, and report/notify the relevant parties of any breaches or incidents related to the study.

The PI role is to complete and to ensure that all relevant regulatory approvals are in place before the study begins. Ensure arrangements are in place for good study conduct, robust monitoring and reporting, including prompt reporting of incidents, this includes putting in place adequate training for study staff to conduct the study as per the protocol and relevant standards.

1. INTRODUCTION

This feasibility study is the natural extension of our recently completed study (R&D 16/0242) which assessed how the use of an Acapella Choice (Smiths Medical) positive expiratory pressure (PEP) device as a semi-occluded vocal tract exercise (SOVTE) impacted acoustic, electroglottographic and aerodynamic measures of the voice in a group of normophonic volunteers. In that study, Acapella Choice was found to offer significantly greater oscillating intraoral pressures than techniques in current clinical practice and was found to have measurable benefits in terms of producing a louder and more economical voice. It offered the largest oscillating pressures, likened to a ‘massage’ of the vocal organs, giving it great therapeutic promise for patients with excess vocal tract tension.

We seek in this study to evaluate the immediate effects of Acapella Choice as a voice exercise in patients with Muscle Tension Dysphonia, Presbylaryngis and Vocal Fold Palsy, and compare this to our currently-used technique of phonation into a tube held under water (henceforward referred to as “Tube”). Patients will be recruited from four weekly Voice Clinics held at the Royal National Throat Nose and Ear Hospital where their diagnosis will be confirmed. They will be invited to attend a single experimental session during which time they will exercise both with Acapella Choice and with Tube. Baseline and outcome voice measures will be taken and a short questionnaire will be completed, eliciting perceptions of the two exercises and any changes which were felt to have resulted from them.

Our previous work suggests that Acapella Choice as a SOVTE may offer significant clinical benefits in terms of improved efficacy of therapy. We suggest that it also offers patients a more convenient and user-friendly form of exercise which may well improve compliance and result in better outcomes.

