3. OBJECTIVES

3.1. Primary Objective

To determine what impact the use of an Acapella Choice device has on the voices of people with voice disorders when it is used as a form of semi-occluded vocal tract exercise.

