3.2. Secondary Objectives

To identify whether this patient group is able to make use of Acapella Choice for this purpose

To identify if this intervention can be incorporated into the standard patient clinical pathway

To identify if sufficient subjects can be recruited and retained

To identify sample sizes for possible future research

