4. STUDY DESIGN

This is a feasibility study using a ‘before and after’ design to test the immediate effects of exercising with Acapella Choice in comparison to the immediate effects of exercising with Tube. Dysphonic subjects will be recruited from referrals received from four RNTNE-based voice clinics with an endoscopically-confirmed diagnosis of muscle tension dysphonia (MTD), presbylaryngis (age-related vocal fold atrophy) or vocal fold palsy. They will attend only one research session which will last approximately one hour.

The aim is to recruit ten subjects from each diagnosis for a total of 30 patients. As this is a feasibility study, a sample size calculation has not been performed. Instead, the target number for recruitment is instead informed by a recent audit of referrals to the department.

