5. STUDY SCHEDULE

Enrolment will begin from day one of the study. Prospective participants will be identified by the Speech Therapist in attendance at voice clinics held at the Royal National Throat Nose and Ear Hospital. The therapist will briefly explain the study, give the patient and information sheet, and get consent for the PI to contact them over the following week to carry out a telephone screening of their eligibility.

Following successful screening by the PI, the participant will be given an appointment to attend an approximately one hour long research session where the interventions will be carried out and data collected. This single session will conclude the participant’s involvement in the study, and they will return to their ordinary clinical pathway, awaiting commencement of their Speech Therapy input, as indicated. There will be no study follow-up for participants.

A participant may withdraw at any time and their normal clinical pathway from referral to treatment will remain unaffected.

The end of the study will be reached as soon as the target number of participants has been recruited, or eighteen months has elapsed from the commencement of the study, whichever comes first.

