9. STATISTICAL METHODS

As this is a feasibility study and this is the first time that this particular exercise has been trialled in pathological voice, effect sizes are as yet unknown. The decision to recruit 10 participants of each voice type was informed by a recent audit of departmental referrals (January 2015 to July 2017). Over this period, we received an average of 57 referrals per month. Monthly referrals for MTD account for 15.8% of that total (9), referrals for vocal fold palsy account for 6.5% (4) and referrals for presbylaryngis account for 5.9% (3). It was felt that 10 of each group was reasonable to recruit within the planned timescale of the study (initially, 12 months, but owing to a significant drop in throughput of patients in voice clinics as a result of Covid-19, this timescale has been extended to 18 months), large enough to inform about the practicalities of recruiting for a larger future study and large enough to provide some indication of the effects of each treatment on baseline variables.

Despite it being unclear what effects will be seen in these clinical populations, our previous pilot using normophonic volunteers was able to identify statistically significant change in sound pressure level (SPL) and mean flow during voicing, both biologically relevant changes for voice production. For this study, descriptive statistics will be used and will include box plots, means/medians, standard error and tests of significant differences between groups and exercises will be carried out using ANOVAs. Baseline data for consideration will include expert-rated perceptual, acoustic, aerodynamic and electroglottographic measures of the voice.

Questionnaire data will also be collected and will be analysed for pre-post changes in self-rated voice quality and ease of voice production. Views on the exercises (i.e. ease of use, portability, likelihood of carrying out task if it were given in a therapy programme) will also be compared between exercises and between groups.

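### Both exercises are done in one session and compared by ANOVA, but the plan does not fix or balance their order, say whether measures are repeated before the second exercise, or name a period term

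*Combined protocol and SAP*

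**What the plan says.** The Introduction describes a within-participant comparison in one visit: "They will be invited to attend a single experimental session during which time they will exercise both with Acapella Choice and with Tube". On measurement it says only "Baseline and outcome voice measures will be taken". Section 4 calls the design before-and-after and gives its purpose as "to test the immediate effects of exercising with Acapella Choice in comparison to the immediate effects of exercising with Tube". Section 5 describes the visit as an "approximately one hour long research session where the interventions will be carried out and data collected".

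Section 9 states that "tests of significant differences between groups and exercises will be carried out using ANOVAs", without listing model terms. It also calls ten per diagnosis "large enough to provide some indication of the effects of each treatment on baseline variables". The primary objective (Section 3.1) is "To determine what impact the use of an Acapella Choice device has on the voices of people with voice disorders".

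None of these sections gives the order of the two exercises, a method of assigning order, a set of measures between them, or an order or period term. Forms of the word randomised occur only in the abbreviation list and in the title of a cited study.

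**The concern.** When one person does two exercises within about an hour, the second is done by a voice that has already been exercised. The protocol's own rationale makes this matter. Both techniques are semi-occluded exercises credited with a massage-like action, and the study expects a single short bout to change the voice at once. People with previous speech therapy input are excluded, so most participants will probably be new to the tasks and practice effects are plausible.

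If everyone followed the same order, any warm-up, practice, fatigue or carry-over would be part of the Acapella-versus-Tube difference, and no later analysis could take it out. If Acapella came second, its own before-after change, which is the primary objective, would be affected too. The aims on recruitment, retention and clinical pathway are largely untouched.

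**Working it through.** **The plan's own figures.** There is no power calculation to reproduce. The target is 3 × 10 = 30. The audit figures check: 57 × 15.8% = 9.0, 57 × 6.5% = 3.7 and 57 × 5.9% = 3.4, which round to the stated 9, 4 and 3 per month.

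**Can exercise and period be separated?** Take a model with 30 participant columns, one for exercise and one for period (32 in all).
- Same order for all 30: rank 31 of 32. Exercise and period are the same column up to sign, so the whole period effect goes into the exercise contrast.
- 15/15 or 20/10 split: rank 32 of 32, so the two can be separated if a period term is fitted.

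If no period term is fitted, the share of the period effect left as bias is (n₁ − n₂)/N. This is 100% at 30/0, 33% at 20/10, 20% at 18/12 and 0% at 15/15.

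**How much could it matter?** The documents give no shift size, SD or significance level, so these inputs are assumptions: no true exercise difference, two-sided 5%, one common order, and SD of the post-minus-post paired difference = 1. A shift s of 0.3 or 0.5 is present when the second exercise starts, and a fraction f of it has faded by the second post measure. Rejection rates come from the non-central t distribution with n − 1 df.

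- One session baseline: the baseline cancels, the contrast is shifted by (1 − f)s, and the non-centrality is (1 − f)s√n. For n=30, f=0: 0.3 × 5.477 = 1.64 and 0.5 × 5.477 = 2.74.
- Measures around each exercise, independent errors: the shift is in the second pre-exercise value, so the change is off by f·s in absolute size and the SD is √2. The non-centrality is f·s√(n/2). For n=30, f=1: 0.3 × 3.873 = 1.16 and 0.5 × 3.873 = 1.94.

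False significance at n=30, for s = 0.3 / 0.5:

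| Fraction faded | One session baseline | Measures around each exercise |
|---|---|---|
| None | 35.5% / 75.4% | 5% / 5% |
| Half | 12.5% / 26.3% | 8.7% / 15.5% |
| All | 5% / 5% | 20.3% / 46.5% |

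Within one diagnosis (n=10), one session baseline and no fading, the rates are 13.6% / 29.3%.

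**After balancing.** With 15/15 order and a period term, 20,000 simulated studies per setting gave a type I error of 4.7% to 5.2% for pure period effects of 0.3 to 0.8 SD. At n=10 split 5/5 it was 4.9% to 5.1%. The 95% half-width goes from t(29)/√30 = 2.045/5.477 = 0.373 SD to t(28)/√30 = 2.048/5.477 = 0.374 SD. At n=10 it goes from 0.715 to 0.729 SD.

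**The case against.** **The detail may exist elsewhere.** Section 14 mentions an experimental protocol and Section 15.2.3 a manual of operation. Neither was supplied, and either may fix the order. This stands: a reader might infer that the comparison is in fact confounded, but the documents show only that the plan permits it.

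**The wording leans towards measures around each exercise.** The before-and-after label and the phrase "large enough to provide some indication of the effects of each treatment on baseline variables" point that way, and on that reading the 36%/75% rates do not apply. This also stands, and is why both columns are shown. But the wording does not settle the timing, and repeating the measures does not by itself protect a common order: the right-hand column reaches 20%/47%.

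**It is a small feasibility study.** This lowers the weight. It does not remove the point, because Section 9 plans significance tests between exercises and the primary objective is an effect on the voice.

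**Future sample sizes.** A reader might infer that the aim "To identify sample sizes for possible future research" is compromised. The documents do not say that observed effects will be used for it, and under a common order a constant shift leaves the SD of the paired difference, a main input, unchanged.

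**Two baselines as bounds.** A reader might infer that analysing against both the session baseline and the pre-exercise values would bracket the true difference. That fails once Tube also carries over, and Section 2 describes Tube as an active exercise. Suppose order is balanced, each exercise carries over 0.5 SD, and Acapella's effect fades by 80% and Tube's by 20%. The residuals at the second post measure are 0.1 and 0.4, so the session-baseline bias is (0.4 − 0.1)/2 = +0.15 SD. The amounts lost are 0.4 and 0.1, so the own-baseline bias is (−0.1 + 0.4)/2 = +0.15 SD. Both have the same sign and size.

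**Conclusion.** The omission is clear in the supplied text. Followed as written, the plan allows a common order, which would make the exercise effect and the order effect inseparable. That is worth fixing before data collection because it cannot be repaired in analysis. Importance is moderate.

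The size is conditional. Under a common order and assumed shifts of 0.3 to 0.5 SD, the false-significance rate at n=30 lies anywhere from the nominal 5% to 75%, according to when measures are taken and how fast the shift fades. The 75% figure is the worst case and not a forecast. It needs a common order, one session baseline, the larger assumed shift and no fading together.

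Balancing the order has limits. It does not remove unequal carry-over. Acapella's own before-after change will still contain warm-up and repeat-testing effects, even in those who do it first, because there is no period without exercise.

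**What to change.** **Sections 4 and 5.** Randomise exercise order in balanced blocks of two within each diagnosis, giving 5/5 per ten. If recruitment stops at 18 months, each diagnosis is then at most one participant out of balance. State when the voice measures and self-ratings are taken, including a set before the second exercise if the session allows.

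**Section 9.** Replace the general reference to ANOVAs with a repeated-measures or mixed model containing participant (random), exercise, diagnosis, exercise-by-diagnosis and period. Participant should be random because fixed participant effects would absorb diagnosis. The interaction is needed to compare how the three voice types respond. State the two limitations given in the verdict.

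If a session script already sets a balanced order and measurement times, bring that text into these sections.

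**Cost.** An order list and one model term, with no extra patients or visits; the 95% half-width rises by about 0.001 SD at n=30. The real cost is time. A full repeat set means further acoustic, aerodynamic, electroglottographic and perceptually rated samples from each participant within a visit of about an hour, and the documents give no timings from which to judge whether it fits.

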2. BACKGROUND AND RATIONALE

The therapeutic use of a semi-occluded vocal tract has a very long history and includes time-honoured techniques such as voiced fricatives, lip trills, tongue trills and even humming. Despite been used for generations by singers, the benefits to the voice were until recently purely anecdotal and their scientific basis unexplored. In the early 2000s, [name] undertook a scientific investigation of the benefits of narrowing the vocal tract, specifically with thin flow-resistant straws. His work¹ concluded that benefits to the voice are derived from a heightened interaction of the vibration source (vocal folds) with the vocal tract to make the voice more economic and to reduce collision forces of the vocal fold tissues. A good review of the phenomenon can be found in Titze 2006².

Another form of SOVTE, initially introduced in Finland in the 1960s, involved phonation through glass tubes in air and glass tubes submerged in water. First written about by [name], it was little used outside of Finland until it was introduced in the English-speaking literature in the mid-2000s⁴. By submerging the distal end of a tube under water, bubbling is generated, adding an oscillatory component to the static intraoral pressure⁵⁻⁸. This pressure modulation by water bubbling has been described as producing a 'massage effect'^{4-6,9-11} on the laryngeal muscles that supposedly counteracts harmful maladaptation such as hyperfunctional phonation. This technique is one of the most commonly used by our department at the Royal National Throat, Nose and Ear Hospital.

Clinical experience has shown that many dysphonic patients respond quite well to a form of SOVTE and it comprises a key part of therapeutic intervention. There is a growing body of recent literature which is investigating what effect these exercises have on the phonation of both healthy subjects and those with voice disorders^{7,10-18}. Various studies have shown that SOVTEs induce a lower laryngeal position^{7,19} (often a marker of a deconstricted vocal tract), a firmer closure at the velopharyngeal port²⁰, a narrowed epilarynx and widened pharynx¹⁹ which contribute to richer harmonics, improved vocal fold closure² - all leading to improved voice quality and laryngeal efficiency.

Vibratory PEP devices, such as Acapella Choice, are traditionally used to mobilize secretions in the treatment of excessive sputum or secretion retention in conditions such as cystic fibrosis and neurogenic diseases^{21,22}. PEP devices are usually composed of a mouthpiece attached to a tube with a distal oscillatory flap that closes and opens with airflow, producing an oscillatory pressure within the airways. They aim to match the frequency of vibration of the ciliary epithelium in the lungs, hence promoting the expectoration of secretions.

A practical limitation for implementing tube-in-water voice exercises is the obvious requirement of an accessible water container. PEP, which offers an alternative source of oscillatory pressure without such requirements, might therefore have potential as a form of SOVTE. It was for this reason that we sought to investigate its potential in voice therapy in our previous study.

Our previous study was the first to investigate the use of a PEP device in voice rehabilitation. We found that Acapella® offered significantly greater oscillatory and static pressures than was obtainable from tube-in-water therapy and was the only exercise to create a significant change in loudness alongside improved vocal economy. As this study involved only participants with healthy voice, it remains to be seen how different categories of pathological voice, i.e. hyperfunctional and hypofunctional, would respond to exercising with Acapella®.

3. OBJECTIVES

3.1. Primary Objective

To determine what impact the use of an Acapella Choice device has on the voices of people with voice disorders when it is used as a form of semi-occluded vocal tract exercise.

3.2. Secondary Objectives

To identify whether this patient group is able to make use of Acapella Choice for this purpose

To identify if this intervention can be incorporated into the standard patient clinical pathway

To identify if sufficient subjects can be recruited and retained

To identify sample sizes for possible future research

4. STUDY DESIGN

This is a feasibility study using a ‘before and after’ design to test the immediate effects of exercising with Acapella Choice in comparison to the immediate effects of exercising with Tube. Dysphonic subjects will be recruited from referrals received from four RNTNE-based voice clinics with an endoscopically-confirmed diagnosis of muscle tension dysphonia (MTD), presbylaryngis (age-related vocal fold atrophy) or vocal fold palsy. They will attend only one research session which will last approximately one hour.

The aim is to recruit ten subjects from each diagnosis for a total of 30 patients. As this is a feasibility study, a sample size calculation has not been performed. Instead, the target number for recruitment is instead informed by a recent audit of referrals to the department.

5. STUDY SCHEDULE

Enrolment will begin from day one of the study. Prospective participants will be identified by the Speech Therapist in attendance at voice clinics held at the Royal National Throat Nose and Ear Hospital. The therapist will briefly explain the study, give the patient and information sheet, and get consent for the PI to contact them over the following week to carry out a telephone screening of their eligibility.

Following successful screening by the PI, the participant will be given an appointment to attend an approximately one hour long research session where the interventions will be carried out and data collected. This single session will conclude the participant’s involvement in the study, and they will return to their ordinary clinical pathway, awaiting commencement of their Speech Therapy input, as indicated. There will be no study follow-up for participants.

A participant may withdraw at any time and their normal clinical pathway from referral to treatment will remain unaffected.

The end of the study will be reached as soon as the target number of participants has been recruited, or eighteen months has elapsed from the commencement of the study, whichever comes first.

